Approximately 250 subjects were planned to be randomized in the study in a 1:1 ratio to SOC or PVS. Historical clinical study data on a similar powered surgical stapler demonstrated a need for staple line interventions in approximately 6% of firings on the pulmonary artery or pulmonary vein. This data also showed an average of 2.6 to 2.9 firings per subject, and it is expected, given differences in device design and procedure, that each subject would have required 2 to 3 firings on the renal vein or renal artery in the current study.

Given that it was expected to have a minimum of 300 firings in each group, the sample size of approximately 250 subjects total was considered adequate for descriptive summarization of the primary performance endpoint, i.e. number and frequency of intra-operative surgical interventions. Assuming an approximate background intervention rate of 6%, the given sample size was to have provided reasonable precision in the estimation of the intervention rate to an expected margin of error for a 95% confidence interval of at most 2.9% for each group.

During development of the protocol with the Notified Body (TUV) following their decision to grant CE mark to the device, a formal hypothesis was not defined for the study; however, to establish that the hemostasis intervention rate of PVS is not increased compared to SOC, an acceptance criterion was developed and a 95% confidence interval for the difference in the proportion of firings requiring interventions for PVS minus SOC will be calculated. The powered vascular stapler will be considered to have acceptable performance if the upper bound of the 95% confidence interval does not exceed 3%.

While the given sample sizes were expected to provide reasonable precision for estimation of the hemostasis intervention rate within each treatment group, the study was not sufficiently powered for demonstrating that the between treatment group comparison could achieve the 3% acceptance criterion. The given sample sizes are not large enough to control expected variability of the difference in rates between groups with a high probability, even if the true intervention rates are equivalent, thus increasing the likelihood of not meeting this acceptance criterion.

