For each of the 5000 iterations, the difference in bootstrap estimated sample proportions (PVS – SOC) will be calculated and these values will be used to estimate the sampling distribution of the difference between PVS and SOC in the proportion of firings requiring intervention. The mean of this sampling distribution will be provided as the point estimate for the difference of the proportion of firings requiring intervention between groups and the one-sided upper-tailed 95% confidence interval limit for the difference will be estimated by the upper 0.95 percentile of this sampling distribution.

A secondary estimate of the proportion of firings requiring intervention will be provided under the assumption of independence of firings within a subject. This will be performed based on the total number of firings and the percentage will be calculated as the number of firings requiring an intervention divided by the total number of firings. The following SAS code will be used to generate two-sided 95% confidence intervals for the individual treatment groups and a one-sided upper-tailed 95% confidence interval for the difference between groups:

```
proc sort data=hemo_interv;
  by TrtGroup descending event;
run;
```

```

*two-sided exact 95% confidence interval for within treatment summary;
proc freq data=hemo_interv order=data;
  tables TrtGroup*event/binomial riskdiff exact;
run;
*one-sided exact 95% confidence interval for between treatment summary;
proc freq data=hemo_interv order=data;
  tables TrtGroup*event/binomial riskdiff alpha=0.10;
  exact riskdiff;
run;

```

This code assumes that the dataset hemo_interv contains one record per firing, the variable ‘TrtGroup’ contains the identifier for randomized treatment group (the SOC group should be listed in the first row of the table), and the variable ‘event’ identifies an occurrence of the primary endpoint with a 1 and no occurrence of the primary endpoint with a 0. The resulting output in the Column 1 Risk Estimates table in the SAS Output Window provides the individual confidence intervals for each treatment group as well as the confidence interval for the difference between groups. The above approach utilizes the exact methodology of Clopper and Pearson for estimation of the confidence intervals within each group as well as the difference between groups.

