Additional summaries will be provided to tabulate the total number of vessels transected as well as the specific type of vessel that was transected – renal artery or renal vein. The specific types of interventions that were performed will also be tabulated by randomized treatment group.

The primary safety endpoint, the occurrence of hemostatic interventions/procedures completed for post-operative bleeding related to the transection of the RA and RV, is measured at the subject level and will be analyzed using the same methodology as described above for independent observations. A similar dataset will be created that contains one record per subject and an indicator for whether or not the subject experienced a post-operative intervention event. The SAS code provided above will be utilized in a similar manner for this analysis.

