Two-sided 95% Confidence Interval for Percent Difference (One-sided 95% CI Upper Limit) for Percent Requiring Transection [2]	xx.x%, xx.x%	xx.x%, xx.x%	xx.x%, xx.x%
	xx.x% (xx.x%)		
Type of Intervention, n (%) [3]			
Additional Stapling	xx (xx.x%)	xx (xx.x%)	xx (xx.x%)
Over-sewing	xx (xx.x%)	xx (xx.x%)	xx (xx.x%)
Compression	xx (xx.x%)	xx (xx.x%)	xx (xx.x%)
Use of Suture	xx (xx.x%)	xx (xx.x%)	xx (xx.x%)
Sealant	xx (xx.x%)	xx (xx.x%)	xx (xx.x%)
Buttress	xx (xx.x%)	xx (xx.x%)	xx (xx.x%)
Use of Energy	xx (xx.x%)	xx (xx.x%)	xx (xx.x%)
Clip Placement	xx (xx.x%)	xx (xx.x%)	xx (xx.x%)
Blood Product Transfusion	xx (xx.x%)	xx (xx.x%)	xx (xx.x%)
Additional Surgical Procedure	xx (xx.x%)	xx (xx.x%)	xx (xx.x%)
Other Intervention	xx (xx.x%)	xx (xx.x%)	xx (xx.x%)
Intervention Category, n (%) [4]			
No Intervention	xx (xx.x%)	xx (xx.x%)	xx (xx.x%)
Hemostasis Controllable	xx (xx.x%)	xx (xx.x%)	xx (xx.x%)
Hemostasis Intervention	xx (xx.x%)	xx (xx.x%)	xx (xx.x%)

[1] Denominator for calculation of percentage is the total number of vessels transected in that group.

[2] Difference is calculated as Powered Vascular Stapler minus Standard of Care Stapler.

[3] Denominator for calculation of percentage is the total number of vessels requiring intervention in that group.

[4] Hemostasis Controllable includes additional stapling, over-sewing, compression, use of suture, sealant, buttress, use of energy, clip placement, or other intervention.
 Hemostasis Intervention includes blood product transfusion and additional surgical procedure.

Table 7
 Post-Operative Interventions or Procedures Related to Renal Artery or Renal Vein Bleeding
 Safety Set

Characteristics	Standard of Care Stapler (N = ##)	Powered Vascular Stapler (N = ##)	Overall (N = ##)
Number of Subjects Requiring Post-Operative Intervention Related to Renal Artery or Renal Vein Bleeding			
n (%) [1]	xx (xx.x%)	xx (xx.x%)	xx (xx.x%)
95% Confidence Interval for Percent	xx.x%, xx.x%	xx.x%, xx.x%	xx.x%, xx.x%
Type of Intervention, n (%) [2]			
Blood Product Transfusion	xx (xx.x%)	xx (xx.x%)	xx (xx.x%)
Additional Surgical Procedure	xx (xx.x%)	xx (xx.x%)	xx (xx.x%)
Other Intervention	xx (xx.x%)	xx (xx.x%)	xx (xx.x%)

[1] Denominator for calculation of percentage is the total number of subjects in that group.
 [2] Denominator for calculation of percentage is the total number of subjects requiring intervention in that group.

Table 8
 Device Usage Details
 Full Analysis Set

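### The SAS note in SAP Section 10.4 yields SOC minus PVS, but the 3% criterion and Table 6 need the upper limit of PVS minus SOC; the event column is also not fixed when SOC has no events

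*SAP*

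**What the plan says.** The acceptance criterion in SAP Section 8 is directional: "a 95% confidence interval for the difference in the proportion of firings requiring interventions for PVS minus SOC will be calculated", and performance is acceptable "if the upper bound of the 95% confidence interval does not exceed 3" percent. Protocol Section 7.4 says the same. In SAP Section 10.4 the bootstrap difference is also PVS minus SOC, with its 0.95 percentile as the one-sided limit. The footnote to the difference rows of Table 6, bootstrap and independent-samples alike, reads "Difference is calculated as Powered Vascular Stapler minus Standard of Care Stapler".

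The SAS code in Section 10.4 serves a different estimate: "A secondary estimate of the proportion of firings requiring intervention will be provided under the assumption of independence of firings within a subject". It sorts "by TrtGroup descending event", runs PROC FREQ with ORDER=DATA, and requests RISKDIFF with ALPHA=0.10 and exact limits. The note below it states that "the SOC group should be listed in the first row of the table". It continues: "The resulting output in the Column 1 Risk Estimates table in the SAS Output Window provides the individual confidence intervals for each treatment group", and names the same table as the source of the between-group interval. The coding of TrtGroup is not given.

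For the primary safety endpoint, with one record per subject, Section 10.4 adds: "The SAS code provided above will be utilized in a similar manner for this analysis".

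**The concern.** There are two faults, both in the same block of code.

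**Direction.** With SOC in row 1, the printed difference and interval are for SOC minus PVS. The quantity the SAP wants is the negated lower limit of that interval. Nothing tells the programmer to change the sign or swap the limits, and Section 10.4 presents the code as generating the upper one-sided limit directly. Copying the printed upper limit into Table 6 would put the wrong tail beside a bootstrap limit that runs the right way, and could reverse the 3% reading of that row.

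**Event column.** With ORDER=DATA, the level of the event variable met first becomes column 1. The sort makes that level 1 only if the first-row group has at least one event. This hardly matters for intra-operative interventions at about 6% of firings. It may matter for post-operative interventions, which are counted per subject and may be rare.

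**Working it through.** **Inputs.** At least 300 firings per group, a 6% background rate, about 250 subjects randomized 1:1 (about 125 per group) and the 3% limit (SAP Section 8). Software convention assumed, because the documents do not state it: RISKDIFF is row 1 minus row 2.

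**The plan's own figure.** 6% of 300 is 18 interventions. The Clopper-Pearson 95% interval for 18/300 is 3.59% to 9.32%, a half-width of 2.86%. This agrees with the stated margin of at most 2.9%.

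**Direction.** If the printed interval for SOC minus PVS is (L, U), the interval for PVS minus SOC is (−U, −L). The required upper limit is therefore −L; the printed upper limit is U.

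The limits below are exact unconditional 90% limits for the unstandardized difference: two 5% tails, each p-value maximised over the nuisance rate. There are 300 firings per arm.

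| PVS events | SOC events | PVS − SOC, lower and upper | Correct upper limit | Printed upper limit | 3% reading |
|---|---|---|---|---|---|
| 36 | 18 | −0.88, 12.84 | +12.8% fails | +0.9% passes | reversed |
| 30 | 18 | −2.88, 10.85 | +10.9% fails | +2.9% passes | reversed |
| 29 | 18 | −3.21, 10.52 | +10.5% fails | +3.2% fails | same |
| 18 | 18 | −6.87, 6.87 | +6.9% fails | +6.9% fails | same |
| 12 | 24 | −10.85, 2.88 | +2.9% passes | +10.9% fails | reversed |

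With this method the limits depend on the counts only through their difference. The reading therefore reverses when the counts differ by 12 or more in either direction: 12/300 = 4 points.

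Wald limits for comparison, 36 against 18: SE = √(0.12×0.88/300 + 0.06×0.94/300) = 2.32 points, and 1.645 × 2.32 = 3.82. The correct upper limit is 6.0 + 3.82 = 9.8%; the printed one is −6.0 + 3.82 = −2.2%. For 12 against 24 the correct limit is −0.8% and the printed one +7.2%. Under Wald limits smaller gaps reverse the reading: PVS 24 against SOC 18 gives 5.4% correct and 1.4% printed.

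**Row order.** An ascending sort of plain labels such as PVS and SOC puts PVS first. That gives the required direction but contradicts the note. The sign therefore depends on a coding choice that the SAP leaves open.

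**Event column, with SOC in row 1.**

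- SOC has events, PVS has none: column 1 is the event, as intended.
- SOC has none, PVS has some: column 1 is the non-event. The printed difference is (1 − p_SOC) − (1 − p_PVS) = p_PVS − p_SOC, so its sign happens to be the wanted one, but the within-group rates are non-event rates.
- Neither arm has events: there is one column and no risk difference.

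For the performance endpoint, P(no SOC event) = 0.94^300 ≈ 9 × 10⁻⁹, which is negligible.

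For the safety endpoint with 125 per arm, SOC 0/125 would print as 100% (97.1% to 100%) instead of 0% (0% to 2.9%). PVS 2/125 would print as 98.4% (94.3% to 99.8%) instead of 1.6% (0.2% to 5.7%).

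The documents give no post-operative event rate, so the next figures assume one, equal in both arms. With a = (1 − q)^125:

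| Assumed q | No SOC event, a | No SOC event and at least one PVS event, a(1 − a) | No event in either arm, a² |
|---|---|---|---|
| 0.5% | 53% | 25% | 29% |
| 1% | 28% | 20% | 8% |
| 2% | 8% | 7% | 0.6% |

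**The case against.** The strongest reply is that the SAP defines the direction wherever a result is reported. Footnote [2] covers the independent-samples row of Table 6, so copying the printed upper limit would breach the SAP's own table shell. What is missing is a programming step, in a secondary analysis, and the bootstrap row is unaffected.

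The error would also be visible. A reversal needs a gap of at least 4 points under the exact method, and it would sit beside group percentages and a bootstrap difference pointing the other way. At PVS 27 against SOC 18 the exact limits are −3.9% and +9.9%, so the 3% limit is missed on either tail. With both true rates at 6%, a gap of 12 or more firings in either direction has probability 4.8%; at 9% for PVS against 6% for SOC it is about 35% (300 independent firings per arm).

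On safety, there is no acceptance limit, Table 7 has no difference row, and a line showing 100% of SOC subjects with an intervention would be hard to miss. The instruction to reuse the code also leaves room to adapt it.

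All of this stands, and it limits the consequences. It does not remove the defect: followed literally, the note delivers a quantity other than the one specified, and a correct result depends on someone noticing.

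**Conclusion.** The concern holds and should be fixed, with limited reach. For performance it touches only the independence-based row of Table 6. There the printed upper limit is the wrong tail and, under exact limits with 300 firings per arm, reverses the 3% reading once the observed gap is 4 points or more. For safety it can replace event rates by non-event rates when SOC has no events, and no risk difference can be produced when neither arm has one.

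Three assumptions carry the figures. First, row 1 minus row 2 is a property of the software. Second, the exact method is the unstandardized unconditional one; the SAP attributes the difference interval to Clopper and Pearson, which does not identify it, and Wald limits lower the gap needed for reversal. Third, the safety probabilities rest on assumed event rates.

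**What to change.** 1. Put PVS in row 1 and state the TrtGroup coding that achieves it. Alternatively, keep SOC in row 1 and define the reported limit as minus the lower limit of the printed interval.
2. Fix event = 1 as column 1 whatever the data, for example with a zero-weight record for each of the four cells and the ZEROS option on the WEIGHT statement.
3. State what Tables 6 and 7 report when one or both arms have no events.
4. Add a programmed check that the printed difference equals the PVS percentage minus the SOC percentage.

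The cost is a few lines of code and two sentences in the SAP. Data collection, sample size and the bootstrap do not change. SAP Section 10.1 requires an amendment for changes to planned analyses, so the correction is best made before the tables are programmed.

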10.4.1 Additional Analysis of Primary Performance Endpoint

In consideration of the types of hemostasis interventions that may be observed and recognizing the differing degrees of severity that exist among the types of interventions, each firing will be further classified into one of the following three categories:

- No interventions: No bleeding or bleeding that stops after initial blotting of staple line;
- Hemostasis controllable: bleeding detected and controlled intra-operatively (additional stapling, over-sewing, clip placement, compression, use of suture, sealant, and/or buttress, and/or use of energy);
- Hemostasis intervention: bleeding that occurs intra-operatively requiring blood or blood product transfusion or an additional surgical procedure (e.g. conversion to open).

The number and percentage of firings in each of these categories will be summarized separately for each treatment group. Hemostasis interventions clearly represent the most significant types of interventions from a device performance and subject safety point of view. This summary will be used to supplement the primary performance endpoint analysis where all interventions, regardless of severity, are grouped together and utilized for assessing the acceptance criterion.

10.5 Plans for Interim Analysis

No interim analyses were planned or performed for this study.

10.6 Handling of Missing Data

All summaries will be performed only on subjects undergoing the surgical procedure and only observed data will be summarized. There will be no imputation of data for early terminated subjects or for missing data within the database.

10.7 Sensitivity Analyses

Analyses of the primary performance and safety endpoints will be replicated on the Per Protocol Set to assess the primary results in the set of subjects with no major protocol violations.

10.8 Subgroup Analysis

No subgroup analyses are planned for this study.

10.9 Assessment of Site Homogeneity

No summaries or adjustments by study site are planned for this study.

10.10 Additional Endpoint Analyses

Device usage details will be summarized with counts and percentages for subjects in whom the device was articulated during the surgical procedure. Summaries will be provided by randomized treatment group and in total. Similar summaries will also be provided for the surgeon satisfaction questionnaire and the surgeon device questionnaire (administered only in PVS cases).

Summary statistics will be provided for the Surgery Task Load Index (Surg-TLX). Surgeons are asked to rate 6 specific components after each surgery performed. The 6 components are – mental fatigue, physical fatigue, hurried/rushed pace, procedure complexity, anxious while performing procedure, and distracting operating environment. Each component is scored on a 0 to 100 scale with lower scores representing a ‘Low’ response on that component and higher scores indicating a ‘High’ response on that component. Summaries will also be provided for an overall score which is calculated as the average of the six components for each surgery.

The total number of protocol deviations will be tabulated by treatment group and in total. Specific types of protocol deviations will also be summarized with counts and percentages. The number and percentage of subjects with at least one protocol deviation will also be summarized.

10.11 Safety Analyses

Safety will be assessed through the incidence of adverse events (AEs) and serious adverse events (SAEs), which will be coded using the Medical Dictionary for Regulatory Activities (MedDRA). The number and percentage of subjects reporting AEs and SAEs will be summarized at the MedDRA system organ class and preferred term level by treatment group and overall. Similar summaries will also be provided for AEs and SAEs related to the study device, as well as for AEs and SAEs related to the study procedure. Related events are those where the relationship is indicated as Possibly, Related, or Unknown. The incidence of AEs will also be summarized by maximum severity. All reported adverse events will be listed.

Appendix: Table Shells and List of Listings to be Generated

Table shells are provided below for all summaries to be generated for this study. Additionally, a list of all listings to be created is provided corresponding to the eCRFs that were used during this study. All fields collected will be listed.

Table 1
 Subject Disposition
 All Subjects

	Standard of Care Stapler	Powered Vascular Stapler	Total
Signed Informed Consent			xx
Randomized	xx	xx	xx
Safety Set	xx (xx.x%)	xx (xx.x%)	xx (xx.x%)
Full Analysis Set	xx (xx.x%)	xx (xx.x%)	xx (xx.x%)
Completed the Study	xx (xx.x%)	xx (xx.x%)	xx (xx.x%)
Discontinued from the Study	xx (xx.x%)	xx (xx.x%)	xx (xx.x%)
Reason for Discontinuation			
Withdrawal of consent	xx (xx.x%)	xx (xx.x%)	xx (xx.x%)
Surgical	xx (xx.x%)	xx (xx.x%)	xx (xx.x%)
Adverse Event	xx (xx.x%)	xx (xx.x%)	xx (xx.x%)
Death	xx (xx.x%)	xx (xx.x%)	xx (xx.x%)
Lost to Follow-up	xx (xx.x%)	xx (xx.x%)	xx (xx.x%)
Site or Study Termination	xx (xx.x%)	xx (xx.x%)	xx (xx.x%)
Other	xx (xx.x%)	xx (xx.x%)	xx (xx.x%)

Note: All percentages are based on the number of subjects in the Safety Set as the denominator.

Table 2
 Subject Demographics
 Full Analysis Set

Characteristics	Standard of Care Stapler (N = ##)	Powered Vascular Stapler (N = ##)	Overall (N = ##)
Race			
White	xx (xx.x%)	xx (xx.x%)	xx (xx.x%)
Black or African American	xx (xx.x%)	xx (xx.x%)	xx (xx.x%)
American Indian or Alaska Native	xx (xx.x%)	xx (xx.x%)	xx (xx.x%)
Native Hawaiian or Other Pacific Islander	xx (xx.x%)	xx (xx.x%)	xx (xx.x%)
Asian	xx (xx.x%)	xx (xx.x%)	xx (xx.x%)
Other	xx (xx.x%)	xx (xx.x%)	xx (xx.x%)
Ethnicity			
Hispanic	xx (xx.x%)	xx (xx.x%)	xx (xx.x%)
Non-Hispanic	xx (xx.x%)	xx (xx.x%)	xx (xx.x%)
Age (years)			
n	xx	xx	xx
Mean	xx.x	xx.x	xx.x
Standard Deviation	x.xxx	x.xxx	x.xxx
Median	xx.x	xx.x	xx.x
Minimum, Maximum	xx.x, xx.x	xx.x, xx.x	xx.x, xx.x
Gender			
Male	xx (xx.x%)	xx (xx.x%)	xx (xx.x%)
Female	xx (xx.x%)	xx (xx.x%)	xx (xx.x%)

Table 3
 Protocol Deviations
 Safety Set

Characteristics	Standard of Care Stapler (N = ##)	Powered Vascular Stapler (N = ##)	Overall (N = ##)
Total Number of Protocol Deviations	xxx	xxx	xxx
Specific Types of Protocol Deviations [1]			
Informed Consent Process	xx (xx.x%)	xx (xx.x%)	xx (xx.x%)
Inclusion/Exclusion Criteria	xx (xx.x%)	xx (xx.x%)	xx (xx.x%)
Randomization	xx (xx.x%)	xx (xx.x%)	xx (xx.x%)
Study Procedure	xx (xx.x%)	xx (xx.x%)	xx (xx.x%)
Visit Out of Window	xx (xx.x%)	xx (xx.x%)	xx (xx.x%)
Other	xx (xx.x%)	xx (xx.x%)	xx (xx.x%)
Sponsor Assessment of Protocol Deviations [1]			
Minor	xx (xx.x%)	xx (xx.x%)	xx (xx.x%)
Major	xx (xx.x%)	xx (xx.x%)	xx (xx.x%)
Number (%) of Subjects With at Least 1 Protocol Deviation [2]	xx (xx.x%)	xx (xx.x%)	xx (xx.x%)

1. Denominator used is the total number of protocol deviations reported.
2. Denominator used is the total number of subjects in the column header.

Table 4
 Surgical Characteristics
 Full Analysis Set

Characteristics	Standard of Care Stapler (N = ##)	Powered Vascular Stapler (N = ##)	Overall (N = ##)
Type of Surgery			
Laparoscopic Nephrectomy	xx (xx.x%)	xx (xx.x%)	xx (xx.x%)
Laparoscopic Nephroureterectomy	xx (xx.x%)	xx (xx.x%)	xx (xx.x%)
Number of Renal Arteries Transected			
0	xx (xx.x%)	xx (xx.x%)	xx (xx.x%)
1	xx (xx.x%)	xx (xx.x%)	xx (xx.x%)
2	xx (xx.x%)	xx (xx.x%)	xx (xx.x%)
3	xx (xx.x%)	xx (xx.x%)	xx (xx.x%)
Number of Ports			
1	xx (xx.x%)	xx (xx.x%)	xx (xx.x%)
2	xx (xx.x%)	xx (xx.x%)	xx (xx.x%)
3	xx (xx.x%)	xx (xx.x%)	xx (xx.x%)
4	xx (xx.x%)	xx (xx.x%)	xx (xx.x%)
Number of Drains Placed Intraoperatively			
0	xx (xx.x%)	xx (xx.x%)	xx (xx.x%)
1	xx (xx.x%)	xx (xx.x%)	xx (xx.x%)
2	xx (xx.x%)	xx (xx.x%)	xx (xx.x%)
ASA Physical Status			
Class I	xx (xx.x%)	xx (xx.x%)	xx (xx.x%)
Class II	xx (xx.x%)	xx (xx.x%)	xx (xx.x%)
Class III	xx (xx.x%)	xx (xx.x%)	xx (xx.x%)

Table 4
 Surgical Characteristics
 Full Analysis Set

Characteristics	Standard of Care Stapler (N = ##)	Powered Vascular Stapler (N = ##)	Overall (N = ##)
Estimated Blood Loss (mL)			
n	xx	xx	xx
Mean	xx.x	xx.x	xx.x
Standard Deviation	x.xxx	x.xxx	x.xxx
Median	xx.x	xx.x	xx.x
Minimum, Maximum	xx.x, xx.x	xx.x, xx.x	xx.x, xx.x
Transfusion of Blood or Blood Product Required?			
Yes	xx (xx.x%)	xx (xx.x%)	xx (xx.x%)
No	xx (xx.x%)	xx (xx.x%)	xx (xx.x%)
Procedure Converted to Open?			
Yes	xx (xx.x%)	xx (xx.x%)	xx (xx.x%)
No	xx (xx.x%)	xx (xx.x%)	xx (xx.x%)
Procedure Duration (min)			
n	xx	xx	xx
Mean	xx.x	xx.x	xx.x
Standard Deviation	x.xxx	x.xxx	x.xxx
Median	xx.x	xx.x	xx.x
Minimum, Maximum	xx.x, xx.x	xx.x, xx.x	xx.x, xx.x
Drain Duration (nights)			
n	xx	xx	xx
Mean	xx.x	xx.x	xx.x
Standard Deviation	x.xxx	x.xxx	x.xxx
Median	xx.x	xx.x	xx.x
Minimum, Maximum	xx.x, xx.x	xx.x, xx.x	xx.x, xx.x

Programming Note: Chest tube duration is calculated from date of surgery to date of final chest tube removal

Table 5
 Tumor Assessment – Pathology Lab
 Full Analysis Set

Characteristics	Standard of Care Stapler (N = ##)	Powered Vascular Stapler (N = ##)	Overall (N = ##)
Tumor Stage, Confirmed by Pathology			
Stage 0	xx (xx.x%)	xx (xx.x%)	xx (xx.x%)
Stage IA	xx (xx.x%)	xx (xx.x%)	xx (xx.x%)
Stage IB	xx (xx.x%)	xx (xx.x%)	xx (xx.x%)
Stage IIA	xx (xx.x%)	xx (xx.x%)	xx (xx.x%)
Stage IIB	xx (xx.x%)	xx (xx.x%)	xx (xx.x%)
Stage IIIA	xx (xx.x%)	xx (xx.x%)	xx (xx.x%)
Stage IIIB	xx (xx.x%)	xx (xx.x%)	xx (xx.x%)
Stage IV	xx (xx.x%)	xx (xx.x%)	xx (xx.x%)
Maximum Tumor Diameter (cm)			
n	xx	xx	xx
Mean	xx.x	xx.x	xx.x
Standard Deviation	x.xxx	x.xxx	x.xxx
Median	xx.x	xx.x	xx.x
Minimum, Maximum	xx.x, xx.x	xx.x, xx.x	xx.x, xx.x
Maximum Tumor Depth (cm)			
n	xx	xx	xx
Mean	xx.x	xx.x	xx.x
Standard Deviation	x.xxx	x.xxx	x.xxx
Median	xx.x	xx.x	xx.x
Minimum, Maximum	xx.x, xx.x	xx.x, xx.x	xx.x, xx.x
Primary Tumor TNM Classification			
TX	xx (xx.x%)	xx (xx.x%)	xx (xx.x%)
T0	xx (xx.x%)	xx (xx.x%)	xx (xx.x%)
Tix	xx (xx.x%)	xx (xx.x%)	xx (xx.x%)
T1	xx (xx.x%)	xx (xx.x%)	xx (xx.x%)
T1a	xx (xx.x%)	xx (xx.x%)	xx (xx.x%)
T1b	xx (xx.x%)	xx (xx.x%)	xx (xx.x%)
T2	xx (xx.x%)	xx (xx.x%)	xx (xx.x%)
T3	xx (xx.x%)	xx (xx.x%)	xx (xx.x%)
T4	xx (xx.x%)	xx (xx.x%)	xx (xx.x%)

Table 5
 Tumor Assessment – Pathology Lab
 Full Analysis Set

Characteristics	Standard of Care Stapler (N = ##)	Powered Vascular Stapler (N = ##)	Overall (N = ##)
TNM Classification for Regional Lymph Node			
NX	xx (xx.x%)	xx (xx.x%)	xx (xx.x%)
N0	xx (xx.x%)	xx (xx.x%)	xx (xx.x%)
N1	xx (xx.x%)	xx (xx.x%)	xx (xx.x%)
N2	xx (xx.x%)	xx (xx.x%)	xx (xx.x%)
N3	xx (xx.x%)	xx (xx.x%)	xx (xx.x%)
Distant Metastasis Present?			
Yes	xx (xx.x%)	xx (xx.x%)	xx (xx.x%)
No	xx (xx.x%)	xx (xx.x%)	xx (xx.x%)
Tumor Confirmed by Pathology as Non-Small Cell Lung Cancer?			
Yes	xx (xx.x%)	xx (xx.x%)	xx (xx.x%)
No	xx (xx.x%)	xx (xx.x%)	xx (xx.x%)

Table 6
 Intra-Operative Interventions on Renal Artery or Renal Vein
 Full Analysis Set

Characteristics	Standard of Care Stapler (N = ##)	Powered Vascular Stapler (N = ##)	Overall (N = ##)
Total Number of Vessels Transected	xxx	xxx	xxx
Renal Artery	xxx	xxx	xxx
Renal Vein	xxx	xxx	xxx
Bootstrap Based Estimate of Number of Vessel Transections Requiring Intervention n (%)	xx (xx.x%)	xx (xx.x%)	xx (xx.x%)
Two-sided 95% Confidence Interval for Percent Difference (One-sided 95% CI Upper Limit) for Percent Requiring Transection [2]	xx.x%, xx.x%	xx.x%, xx.x%	xx.x%, xx.x%
	xx.x% (xx.x%)		
Independent Samples Estimate of Number of Vessel Transections Requiring Intervention [1] n (%)	xx (xx.x%)	xx (xx.x%)	xx (xx.x%)
Two-sided 95% Confidence Interval for Percent Difference (One-sided 95% CI Upper Limit) for Percent Requiring Transection [2]	xx.x%, xx.x%	xx.x%, xx.x%	xx.x%, xx.x%
	xx.x% (xx.x%)		
Type of Intervention, n (%) [3]			
Additional Stapling	xx (xx.x%)	xx (xx.x%)	xx (xx.x%)
Over-sewing	xx (xx.x%)	xx (xx.x%)	xx (xx.x%)
Compression	xx (xx.x%)	xx (xx.x%)	xx (xx.x%)
Use of Suture	xx (xx.x%)	xx (xx.x%)	xx (xx.x%)
Sealant	xx (xx.x%)	xx (xx.x%)	xx (xx.x%)
Buttress	xx (xx.x%)	xx (xx.x%)	xx (xx.x%)
Use of Energy	xx (xx.x%)	xx (xx.x%)	xx (xx.x%)
Clip Placement	xx (xx.x%)	xx (xx.x%)	xx (xx.x%)
Blood Product Transfusion	xx (xx.x%)	xx (xx.x%)	xx (xx.x%)
Additional Surgical Procedure	xx (xx.x%)	xx (xx.x%)	xx (xx.x%)
Other Intervention	xx (xx.x%)	xx (xx.x%)	xx (xx.x%)
Intervention Category, n (%) [4]			
No Intervention	xx (xx.x%)	xx (xx.x%)	xx (xx.x%)
Hemostasis Controllable	xx (xx.x%)	xx (xx.x%)	xx (xx.x%)
Hemostasis Intervention	xx (xx.x%)	xx (xx.x%)	xx (xx.x%)

[1] Denominator for calculation of percentage is the total number of vessels transected in that group.

[2] Difference is calculated as Powered Vascular Stapler minus Standard of Care Stapler.

[3] Denominator for calculation of percentage is the total number of vessels requiring intervention in that group.

[4] Hemostasis Controllable includes additional stapling, over-sewing, compression, use of suture, sealant, buttress, use of energy, clip placement, or other intervention.
 Hemostasis Intervention includes blood product transfusion and additional surgical procedure.

Table 7
 Post-Operative Interventions or Procedures Related to Renal Artery or Renal Vein Bleeding
 Safety Set

Characteristics	Standard of Care Stapler (N = ##)	Powered Vascular Stapler (N = ##)	Overall (N = ##)
Number of Subjects Requiring Post-Operative Intervention Related to Renal Artery or Renal Vein Bleeding			
n (%) [1]	xx (xx.x%)	xx (xx.x%)	xx (xx.x%)
95% Confidence Interval for Percent	xx.x%, xx.x%	xx.x%, xx.x%	xx.x%, xx.x%
Type of Intervention, n (%) [2]			
Blood Product Transfusion	xx (xx.x%)	xx (xx.x%)	xx (xx.x%)
Additional Surgical Procedure	xx (xx.x%)	xx (xx.x%)	xx (xx.x%)
Other Intervention	xx (xx.x%)	xx (xx.x%)	xx (xx.x%)

[1] Denominator for calculation of percentage is the total number of subjects in that group.
 [2] Denominator for calculation of percentage is the total number of subjects requiring intervention in that group.

Table 8
 Device Usage Details
 Full Analysis Set

Characteristics	Standard of Care Stapler (N = ##)	Powered Vascular Stapler (N = ##)	Overall (N = ##)
Number of Subjects Where Device Was Articulated	xxx	xxx	xxx
Did Articulation Make it Easier to Perform Surgery? [1]			
Yes	xx (xx.x%)	xx (xx.x%)	xx (xx.x%)
No	xx (xx.x%)	xx (xx.x%)	xx (xx.x%)
Was Articulation Essential to Performing the Surgery? [1]			
Yes	xx (xx.x%)	xx (xx.x%)	xx (xx.x%)
No	xx (xx.x%)	xx (xx.x%)	xx (xx.x%)
Was the Angle Range of the Device Sufficient? [1]			
Yes	xx (xx.x%)	xx (xx.x%)	xx (xx.x%)
No	xx (xx.x%)	xx (xx.x%)	xx (xx.x%)

1. Denominator used is the total number of subjects in whom the device was articulated.

Table 9
 Surgery Task Load Index (SURG-TLX)
 Full Analysis Set

Characteristic	Standard of Care Stapler (N = ##)	Powered Vascular Stapler (N = ##)	Overall (N = ##)
Overall Score			
n	xx	xx	xx
Mean	xx.x	xx.x	xx.x
Standard Deviation	x.xxx	x.xxx	x.xxx
Median	xx.x	xx.x	xx.x
Minimum, Maximum	xx.x, xx.x	xx.x, xx.x	xx.x, xx.x
Mentally Fatiguing			
n	xx	xx	xx
Mean	xx.x	xx.x	xx.x
Standard Deviation	x.xxx	x.xxx	x.xxx
Median	xx.x	xx.x	xx.x
Minimum, Maximum	xx.x, xx.x	xx.x, xx.x	xx.x, xx.x
Physically Fatiguing			
n	xx	xx	xx
Mean	xx.x	xx.x	xx.x
Standard Deviation	x.xxx	x.xxx	x.xxx
Median	xx.x	xx.x	xx.x
Minimum, Maximum	xx.x, xx.x	xx.x, xx.x	xx.x, xx.x
Similar summaries for remaining components: Hurried/Rushed Pace Procedure Complexity Anxious While Performing Procedure Distracting Operating Environment			

Note: Each component is scored on a 0 to 100 scale with lower scores representing a 'Low' response and higher scores representing a 'High' response.

Table 10
 Surgeon Satisfaction Questionnaire
 Full Analysis Set

Characteristics	Standard of Care Stapler (N = ##)	Powered Vascular Stapler (N = ##)	Overall (N = ##)
How Satisfied Were You With Device Usability?			
Very Unsatisfied	xx (xx.x%)	xx (xx.x%)	xx (xx.x%)
Unsatisfied	xx (xx.x%)	xx (xx.x%)	xx (xx.x%)
Neutral	xx (xx.x%)	xx (xx.x%)	xx (xx.x%)
Satisfied	xx (xx.x%)	xx (xx.x%)	xx (xx.x%)
Very Satisfied	xx (xx.x%)	xx (xx.x%)	xx (xx.x%)
Amount of Tissue Slippage			
No Tissue Slippage	xx (xx.x%)	xx (xx.x%)	xx (xx.x%)
Some Tissue Slippage	xx (xx.x%)	xx (xx.x%)	xx (xx.x%)
Extensive Tissue Slippage	xx (xx.x%)	xx (xx.x%)	xx (xx.x%)

Table 11
 Surgeon Device Questionnaire
 Full Analysis Set

Question Response	Powered Vascular Stapler (N = ##)
The ECHELON FLEX Powered Vascular Stapler with Advanced Placement Tip enables easier placement of the device on vessels compared to your current standard of care device:	
Strongly Disagree	xx (xx.x%)
Slightly Disagree	xx (xx.x%)
Neutral	xx (xx.x%)
Agree	xx (xx.x%)
Strongly Agree	xx (xx.x%)
The ECHELON FLEX Powered Vascular Stapler with Advanced Placement Tip has the potential to reduce the amount of dissection required (otomy) around the vessel to place the stapler compared to your current standard of care device:	
Strongly Disagree	xx (xx.x%)
Slightly Disagree	xx (xx.x%)
Neutral	xx (xx.x%)
Agree	xx (xx.x%)
Strongly Agree	xx (xx.x%)
The ECHELON FLEX Powered Vascular Stapler with Advanced Placement Tip has the potential to reduce the surgeon stress during the most challenging step of the procedure, which is the renal artery/renal vein transection, compared to your current standard of care device:	
Strongly Disagree	xx (xx.x%)
Slightly Disagree	xx (xx.x%)
Neutral	xx (xx.x%)
Agree	xx (xx.x%)
Strongly Agree	xx (xx.x%)
The ECHELON FLEX Powered Vascular Stapler with Advanced Placement Tip allows for the precise control and placement of the end effector on the target vessel compared to your current standard of care device:	
Strongly Disagree	xx (xx.x%)
Slightly Disagree	xx (xx.x%)
Neutral	xx (xx.x%)
Agree	xx (xx.x%)
Strongly Agree	xx (xx.x%)

Table 12
 Adverse Events by System Organ Class and Preferred Term
 Safety Set

System Organ Class	Preferred Term	Standard of Care Stapler (N = ##)	Powered Vascular Stapler (N = ##)	Overall (N = ##)
Total		xx (xx.x%)	xx (xx.x%)	xx (xx.x%)
System Organ Class 1	Preferred Term 1	xx (xx.x%)	xx (xx.x%)	xx (xx.x%)
	Preferred Term 2	xx (xx.x%)	xx (xx.x%)	xx (xx.x%)
	Preferred Term 3	xx (xx.x%)	xx (xx.x%)	xx (xx.x%)
System Organ Class 2	Preferred Term 1	xx (xx.x%)	xx (xx.x%)	xx (xx.x%)
	Preferred Term 2	xx (xx.x%)	xx (xx.x%)	xx (xx.x%)
System Organ Class 3	Preferred Term 1	xx (xx.x%)	xx (xx.x%)	xx (xx.x%)
	Preferred Term 2	xx (xx.x%)	xx (xx.x%)	xx (xx.x%)
	Preferred Term 3	xx (xx.x%)	xx (xx.x%)	xx (xx.x%)
System Organ Class 4	Preferred Term 1	xx (xx.x%)	xx (xx.x%)	xx (xx.x%)
	Preferred Term 2	xx (xx.x%)	xx (xx.x%)	xx (xx.x%)

The following tables will have the same format as Table 12:

Table 13	Serious Adverse Events by System Organ Class and Preferred Term Safety Set
Table 14	Adverse Events Related to the Study Device by System Organ Class and Preferred Term Safety Set
Table 15	Serious Adverse Events Related to the Study Device by System Organ Class and Preferred Term Safety Set
Table 16	Adverse Events Related to the Study Procedure by System Organ Class and Preferred Term Safety Set
Table 17	Serious Adverse Events Related to the Study Procedure by System Organ Class and Preferred Term Safety Set

Table 18
 Adverse Events by System Organ Class, Preferred Term and Maximum Severity
 Safety Set

System Organ Class	Preferred Term	Standard of Care Stapler (N = ##)	Powered Vascular Stapler (N = ##)	Overall (N = ##)
Total		xx (xx.x%)	xx (xx.x%)	xx (xx.x%)
Mild		xx (xx.x%)	xx (xx.x%)	xx (xx.x%)
Moderate		xx (xx.x%)	xx (xx.x%)	xx (xx.x%)
Severe		xx (xx.x%)	xx (xx.x%)	xx (xx.x%)
System Organ Class 1		xx (xx.x%)	xx (xx.x%)	xx (xx.x%)
Mild		xx (xx.x%)	xx (xx.x%)	xx (xx.x%)
Moderate		xx (xx.x%)	xx (xx.x%)	xx (xx.x%)
Severe		xx (xx.x%)	xx (xx.x%)	xx (xx.x%)
	Preferred Term 1	xx (xx.x%)	xx (xx.x%)	xx (xx.x%)
	Mild	xx (xx.x%)	xx (xx.x%)	xx (xx.x%)
	Moderate	xx (xx.x%)	xx (xx.x%)	xx (xx.x%)
	Severe	xx (xx.x%)	xx (xx.x%)	xx (xx.x%)
	Preferred Term 2	xx (xx.x%)	xx (xx.x%)	xx (xx.x%)
	Mild	xx (xx.x%)	xx (xx.x%)	xx (xx.x%)
	Moderate	xx (xx.x%)	xx (xx.x%)	xx (xx.x%)
	Severe	xx (xx.x%)	xx (xx.x%)	xx (xx.x%)
System Organ Class 2		xx (xx.x%)	xx (xx.x%)	xx (xx.x%)
Mild		xx (xx.x%)	xx (xx.x%)	xx (xx.x%)
Moderate		xx (xx.x%)	xx (xx.x%)	xx (xx.x%)
Severe		xx (xx.x%)	xx (xx.x%)	xx (xx.x%)
	Preferred Term 1	xx (xx.x%)	xx (xx.x%)	xx (xx.x%)
	Mild	xx (xx.x%)	xx (xx.x%)	xx (xx.x%)
	Moderate	xx (xx.x%)	xx (xx.x%)	xx (xx.x%)
	Severe	xx (xx.x%)	xx (xx.x%)	xx (xx.x%)

The following listings will be generated for this study:

Listing 1	Inclusion/Exclusion Criteria All Subjects
Listing 2	Demographics All Subjects
Listing 3	Medical History All Subjects
Listing 4	Surgical History All Subjects
Listing 5	Inclusion/Exclusion at Surgery and ASA Status All Subjects
Listing 6	Procedure Details All Subjects
Listing 7	Procedure Time Duration All Subjects
Listing 8	Intra-Operative Interventions on Renal Artery and Renal Vein All Subjects
Listing 9	Intra-Operative Interventions Not on Renal Artery and Renal Vein All Subjects
Listing 10	Device Usage Details All Subjects
Listing 11	Tumor Assessment Log All Subjects
Listing 12	Surgeon Device Questionnaire (PVS Only) All Subjects
Listing 13	Surgery Task Load Index All Subjects
Listing 14	Surgeon Satisfaction Questionnaire All Subjects
Listing 15	Post-Operative Interventions on Renal Artery and Renal Vein All Subjects

Listing 16	Drain Details Log All Subjects
Listing 17	Adverse Events All Subjects
Listing 18	Concomitant Medications All Subjects
Listing 19	Concomitant Procedures/Interventions All Subjects
Listing 20	Protocol Deviations All Subjects
Listing 21	Completion/Withdrawal All Subjects
Listing 22	Study Visits All Subjects
